### ***Analysis of Efficacy of Omegaven™***

The primary outcome to gain preliminary evidence of efficacy will be based on the time from baseline to normalization of bilirubin level, i.e, first time point among three consecutive in which bilirubin is  $< 2\text{ mg/dL}$ . We do not anticipate that any subject will present a rebound on direct bilirubin after normalization. However, we will describe the cohort with respect to the frequency of rebounds in bilirubin levels.

Crude comparisons of time to normalize direct bilirubin levels using Omegaven™ Results of these analysis will be compared with results of analysis excluding subjects who die or are transplanted. Time to reach a total bilirubin of 1.2 will also be compared using survival analysis methods. Analysis of this outcome will proceed as described for direct bilirubin.

We will also describe individual profiles over time (i.e., 2 months before baseline or birth until end of follow-up period) for all subjects using graphical methods. Trends in liver function markers over time will be explored using generalized linear models in which correlations of observations within subjects will be accounted using a generalized equations or random effects approach. In these models we will hypothesize that for both groups biochemical levels increase for all tests with equal slope before treatment. After treatment, however, levels should be decreasing for patients in the Omegaven™ group. We will perform these analyses including only subjects who did not die or undergo transplantation and including all subjects but assigning for subjects who died or underwent a transplant their worse possible outcome after they died or had the transplant. Using descriptive statistics, we will also explore the association between spikes in blood tests over time and predictors including transfusions of red blood cell products and blood stream infections.

Assessment of efficacy will be also based on comparison of means (or medians) of the mean and maximum modified PELD scores of each subject across all follow-up weeks. Adjustments of these comparisons for potential confounders will be based on linear regression models. Mean rates of infection will be compared. Liver transplant, mortality, and red blood cell product transfusion events will be collected.

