#### Hypothesis for Aim 2:

2.1 – Our primary hypothesis is that, after reaching bilirubin levels  $> 2.5$  mg/dL, patients receiving Omegaven™ will reach a bilirubin level  $\leq 2$  mg/dL faster than patients receiving conventional fat emulsions. Additionally, patients receiving Omegaven™ will experience a decrease in their levels of bilirubin and other hepatic enzymes over time.

2.2 – Patients with surgical gastrointestinal disease and cholestasis will improve clinical hepatic status.

2.3 – Since patients receiving Omegaven™ will have improved immune function, they will have a lower infection rate than patients receiving conventional fat emulsions.

2.4 – Due to a better general hepatic condition, patients receiving Omegaven™ will also experience lower occurrence of liver transplant, death from hepatic associated causes, and blood transfusions.

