## 5.0 Enrollment/Randomization

NICU attendings will screen their patients for infants who need prolonged parenteral nutrition (TPN) and have Parenteral Nutrition Associated Liver Disease. The attending physician will ask the family if they would like more information about the study. [name] will be notified of these infants, and assess if they are suitable candidates. [name] or the NICU research nurses will explain the study to the infant's parents / legal guardians and obtain informed consent in the NICU at Vanderbilt Children's Hospital.

Assessment of the effect of treatment will be based on a non-randomized, open-labeled, prospective study of intravenously administered Omegaven™ fat emulsion to determine safety and preliminary efficacy in the treatment of PN associated liver injury.

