## Details of Omegaven™ Administration

After baseline labs are obtained (Table 2 and 3), therapy with Omegaven™ will be initiated at the goal dose of 1 gram /kg/day and is infused over 12-24 hours. Omegaven™ will be infused intravenously through either a central or peripheral catheter alone or in conjunction with parenteral nutrition. If additional fat calories are needed, they will be provided via the enteral route.. The same standards of care provided to all patients receiving parenteral nutrition solution will be followed. Routine nutritional monitoring is described in Table 3.

Table 2: Suggested Schedule Safety Monitoring for Omegaven™ Therapy

(To be done baseline pre-Omegaven™ therapy and weekly until direct bilirubin <0.4 mg/dL)

Parameter	Baseline	Biweekly	Monthly
Essential Fatty Acid Profile	X		X
PT	X	X	
PTT	X	X	
INR	X	X	

Table 3: Suggested Monitoring Schedule for Omegaven™ Therapy  
(Amended December 26, 2006)

Parameter	Baseline (pre- Omegav- en)	Dail y	Q week * -	Periodicall y**
Weight	X	X		
Fluid balance	X	X		
Vital Signs	X	X		
Catheter site/function	X	X		
Laboratory test:				
Sodium	X		X	
Potassium	X		X	
Chloride	X		X	
Glucose	X		X	
BUN	X		X	
Creatinine	X		X	
Triglycerides	X		X	
Calcium	X		X	
Magnesium	X		X	
Phosphorus	X		X	
Prealbumin	X		X	
C reactive protein	X		X	
Albumin	X		X	
Total protein	X		X	
SGPT	X		X	
Alkaline phosphatase	X		X	
Bilirubin (total and direct)	X		X	

GGT	X		X	
AST	X		X	
Copper				X
Iron				X
Vitamins A,D,E				X
Essential Fatty Acid Profile	X		X	
Free cholesterol	X		X	
Free fatty acids	X		X	
Lipid Panel	X		X	
Hemoglobin	X		X	
Hematocrit	X		X	
RBC	X		X	
WBC	X		X	
Platelets	X		X	
PT	X		X	
PTT	X		X	
INR	X		X	
Fibrinogen				
Selenium				X
Zinc				X
Carnitine				X
Aluminum				X
Retinol binding protein (check when getting Vit A)				X

\* More often as necessitated by clinical course; may be reduced in patients who are stable and whose biochemical markers have improved. Refer to protocol for additional information

In the event that a patient is unable to achieve adequate calories parenterally and is unable to tolerate enteral feeds, it may be necessary to evaluate whether or not the patient should continue the study with Omegaven™ as monotherapy or resume therapy with conventional fat emulsions so that additional parenteral fat calories can be given. The clinical team, in conjunction with the patient's primary physician, will determine if the patient should be removed from the protocol. The DSMB will also be notified.

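### The time-to-normalisation endpoint depends on how often bilirubin is tested, and the plan gives no testing schedule for the comparator group

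*Combined protocol and SAP*

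**What the plan says.** Section 10.0 (Analysis of Efficacy) sets the primary efficacy event at the "first time point among three consecutive in which bilirubin is" below 2 mg/dL. It states no interval between the three values, no visit window and no minimum time below the threshold.

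Hypothesis 2.1 in section 2.0, labelled primary, is that Omegaven patients will reach the target "faster than patients receiving conventional fat emulsions". Section 5.0 says: "Assessment of the effect of treatment will be based on a non-randomized, open-labeled, prospective study". The efficacy section relies on a second group ("In these models we will hypothesize that for both groups biochemical levels" rise at the same rate before treatment), but the source, size, follow-up and testing of that group are not described. Survival methods are named for total bilirubin of 1.2, to be handled as for direct bilirubin. No model and no effect measure are named.

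Bilirubin appears as a weekly test in Table 3 of section 6.0, headed "Suggested Monitoring Schedule for Omegaven™ Therapy". Its footnote reads "More often as necessitated by clinical course; may be reduced in patients who are stable and whose biochemical markers have improved". The heading of Table 2 says "weekly until direct bilirubin <0.4 mg/dL", but that table has no bilirubin row and its columns are biweekly and monthly. The safety part of section 10.0 lists routine direct bilirubin among outcomes measured in the Omegaven group; its list for both groups omits bilirubin.

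**The concern.** An event defined by three consecutive values is sensitive to test frequency in two ways. First, a fall below 2 mg/dL is seen only at the next test, on average half an interval late. Second, the event counts only if two further low tests follow before follow-up ends. With sparse testing, infants who normalise late in follow-up are censored instead of counted as events. Conversely, where tests are dense, three values within a few days can satisfy the rule during a short dip.

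If the groups are tested at different rates, the comparison in hypothesis 2.1 mixes treatment effect with test frequency. Allocation is not randomised, so nothing in the design equalises testing. The limitations paragraph raises misclassification only because direct bilirubin is an imperfect marker of liver function; it does not mention test frequency.

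**Working it through.** **1. Plan figure to reproduce.** None. The documents state no sample size, power, significance level, event count or hazard ratio.

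**2. Inputs.** From the plan: three consecutive values below 2 mg/dL, event dated at the first; weekly suggested testing on Omegaven, adjustable in both directions; PN expected for at least 30 more days at entry (section 4.0); at least 2 months of follow-up after treatment stops (section 6.0). Assumed, because the plan is silent: control test interval, distribution of true time to normalisation, and total follow-up.

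**3. Confirmation span.** With interval d, three tests span 2d. With follow-up F, the last test that can start a confirmed run is at F − 2d.

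| Interval d (weeks) | Span 2d | Last start, F = 12 | F = 16 | F = 26 |
|---|---|---|---|---|
| 1 | 2 | 10 | 14 | 24 |
| 2 | 4 | 8 | 12 | 22 |
| 4 | 8 | 4 | 8 | 18 |

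A short follow-up suggested by the plan's own periods is 30 + 60 = 90 days, or 90/7 = 12.9 weeks. With tests counted from baseline, the last usable start is then week 10, 8 or 4. An infant who normalises at week 6 counts under the first two schedules and never under the third.

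**4. Proportion confirmed, by formula.** Assume exponential time to sustained normalisation with median 9 weeks, F = 16, and a first test at random within the first interval. The last usable start g is then uniform between F − 3d and F − 2d, and the proportion confirmed is 1 minus the average of 2^(−g/9).
- True proportion below 2 by week 16: 1 − 2^(−16/9) = 0.71.
- Weekly, g from 13 to 14: about 1 − 2^(−13.5/9) = 0.65.
- 2-weekly, g from 10 to 12: about 1 − 2^(−11/9) = 0.57.
- 4-weekly, g from 4 to 8: 1 − (9/ln 2)(2^(−4/9) − 2^(−8/9))/4 = 1 − 12.98 × 0.195/4 = 0.37.

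Simulation of the same case gave 0.64, 0.57 and 0.36.

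**5. Spurious hazard ratio, by simulation.** Both groups have the same true courses (medians of 6, 9 or 14 weeks) and differ only in testing. The event is dated as written. The analysis is a Cox model with 3,000 to 8,000 infants per group. The ranges for fixed schedules, except daily testing, include runs with assay noise and transient spikes (median 9 weeks, follow-up 16 and 26 weeks). The 14-week median was not run at 52 weeks.

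| Omegaven tests | Control tests | Follow-up (weeks) | Hazard ratio |
|---|---|---|---|
| weekly | weekly | 12–52 | 0.96–1.05 |
| weekly | 2-weekly | 12–52 | 1.04–1.33 |
| weekly | 4-weekly | 16–52 | 1.13–2.18 |
| weekly | 4-weekly | 12 | 4.1–4.9 |
| weekly | twice weekly | 12–52 | 0.87–0.98 |
| weekly | daily | 12–52 | 0.79–0.97 |
| weekly, then 2- or 4-weekly after first value below 2 | weekly | 12–26 | 0.42–0.94 |

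In the last row (median 9 weeks), thinning to 4-weekly gives 0.42, 0.64 and 0.87 at 12, 16 and 26 weeks; thinning to 2-weekly gives 0.86, 0.90 and 0.94.

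**6. A second model.** Here bilirubin declines from an assumed median of 6 mg/dL with a median half-life of 6 weeks and 10% noise, and follow-up is 30 days plus an exponential time plus 2 months. In truth 85% fall below 2. Confirmed: 78% with weekly tests, 69% with 2-weekly, 43% with 4-weekly. The hazard ratio for weekly against 2-weekly is 1.23, and against 4-weekly 2.33. On a common 4-weekly grid it is 1.02. In a similar model, lengthening the mean of the exponential part from 8 to 30 weeks cuts these ratios from 1.24 to 1.10 and from 2.24 to 1.48.

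**The case against.** - **Control testing may be the same.** The text before Table 2 says that the usual standards of care for PN patients apply, and calls Table 3 routine nutritional monitoring. Similar testing in soybean infants is therefore not excluded, and with equal schedules the ratio is about 1. This stands as a limit on the claim, but no sentence applies Table 3 to the comparator.
- **A time point may mean a weekly visit.** The endpoint uses that word, and the modified PELD score is summarised over follow-up weeks. The reading is possible. It would still need stating, because the schedule is only suggested and the footnote lets it vary.
- **Confirmation does not delay the event date.** This is correct: the event is dated at the first value, so confirmation costs events only near the end of follow-up. The bias shrinks as follow-up lengthens, as steps 5 and 6 show.
- **No hazard ratio is planned.** True. It is used here only to express the size of the distortion, which would affect any survival comparison of these event times.
- **A stronger reading.** A reader might infer that the plan is tilted towards Omegaven by a known amount, because Table 3 is titled for Omegaven. The documents do not support that. The control interval is not given, and the footnote allows thinning in exactly the improved infants who still need low values confirmed. No post-treatment testing schedule is given either. Each of these can push the ratio below 1.

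**Conclusion.** The concern holds as a dependence of the primary efficacy comparison on test frequency, with unknown direction. What the documents establish is the rule without spacing or duration, the adjustable schedule titled for Omegaven, the missing comparator schedule, and the between-group claim.

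The size rests on assumptions. If controls were tested every 2 to 4 weeks, Omegaven infants weekly, and follow-up is about 16 weeks or more, identical courses give a hazard ratio of about 1.0 to 2.3. At 12 weeks, 4-weekly control testing gives more than 4. If controls were tested more often, or Omegaven tests are thinned after improvement, the ratio is about 0.4 to 0.98, the lowest value arising with 12 weeks of follow-up and thinning to 4-weekly. Equal testing, or a common grid, brings it back to about 1. This should be corrected before the groups are compared.

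**What to change.** Define the endpoint in section 10.0 on calendar time, identically in both groups:
- Take one bilirubin value per fixed interval, by a pre-stated selection rule, and define normalisation as three consecutive grid points below 2 mg/dL, dated at the first. Set the interval to the finest that both groups' records support, decided from test dates without looking at outcomes.
- Alongside it, report an interval-censored time-to-event analysis that uses all values.
- Tabulate bilirubin tests per infant-week by group, and state how the comparator was tested and followed.

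The cost is SAP wording and modest programming. No new blood tests are needed. The downside is real if the grid must be coarse: event dates are less precise, some values go unused, and fewer events are confirmed (78% falls to 43% when weekly becomes 4-weekly in the second model). The interval-censored analysis offsets this because it discards no values.

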## 4.0 Inclusion/Exclusion Criteria

### Inclusion Criteria:

1. Patients aged 0 to 2 years will be PN dependent (unable to meet nutritional needs solely by enteral nutrition) and are expected to require PN for at least another 30 days
2. Patients considered eligible for study participation must have parenteral nutrition associated liver disease (PNALD) as defined as a direct bilirubin of >2.5 mg/dl or more. Other causes of liver disease should be excluded. A liver biopsy is not necessary for treatment.
3. Signed patient informed consent.

4. The patient must have utilized standard therapies to prevent the progression of his/her liver disease including surgical treatment, cyclic PN, avoiding overfeeding, reduction/removal of copper and manganese from PN, advancement of enteral feeding, and the use of ursodiol (i.e., Actigall®).

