#### Exclusion Criteria:

1. Other causes of chronic liver disease (Hepatitis C, Cystic fibrosis, biliary atresia, and alpha 1 anti-trypsin deficiency,)
2. Enrollment in any other clinical trial involving an investigational agent (unless approved by the designated physicians on the multidisciplinary team)
- 3.. The parent or guardian or child unwilling to provide consent or assent
4. Patients with severe hemorrhagic disorders
5. Patients with severe liver disease not caused by prolonged PN and renal insufficiency
6. Patients with uncontrolled diabetes mellitus

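### The primary time-to-normalization comparison is unadjusted for starting bilirubin, so any difference between the groups at entry can look like a treatment effect, in either direction

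*Combined protocol and SAP*

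**What the plan says.** - **Entry.** Section 4.0, inclusion item 2, sets liver disease "as defined as a direct bilirubin of >2.5 mg/dl or more". Neither criteria list sets an upper limit. The nearest exclusion, "Patients with severe liver disease not caused by prolonged PN and renal insufficiency", works by cause and not by bilirubin level.
- **Endpoint.** Section 10.0 (efficacy analysis) times each infant from baseline to the "first time point among three consecutive in which bilirubin is" below 2 mg/dL.
- **Hypothesis.** Hypothesis 2.1 in Section 2.0 is between groups: after exceeding 2.5 mg/dL, Omegaven patients will reach 2 mg/dL or less "faster than patients receiving conventional fat emulsions".
- **Allocation.** Sections 2.0 and 5.0 describe a non-randomized, open-label study.
- **Analysis.** For this outcome Section 10.0 offers "Crude comparisons of time to normalize direct bilirubin levels", to be set beside an analysis without infants who die or are transplanted. Time to a total bilirubin of 1.2 is to be analysed in the same way.
- **Adjustment.** "Adjustments of these comparisons for potential confounders will be based on linear regression models" directly follows the comparison of modified PELD scores and refers to it.
- **Data available.** Table 3 in Section 6.0 lists "Bilirubin (total and direct") at baseline and weekly.
- **Limitations.** The limitations paragraph names misclassification only, not imbalance at entry.

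**The concern.** With a fixed target, the distance to travel is set by where the infant starts. At the entry floor the required fall is 0.5 mg/dL; above it the distance has no bound. Nothing in a non-randomized design makes the Omegaven and soybean-emulsion groups start at the same level. Standard therapies must also have been used before entry, so an infant may enrol well above the floor. An unadjusted comparison of times then mixes severity at entry with any effect of the emulsion. At stake is the primary efficacy outcome, and the total bilirubin outcome inherits the same analysis.

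**Working it through.** The plan states no sample size, effect size, event count or baseline distribution, so there is no figure of its own to reproduce. The check has two steps, and everything beyond the two thresholds is an assumption.

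**Step 1: dependence on the starting value.** From the plan: floor 2.5 and target 2 mg/dL. Gap at the floor: 2.5 − 2.0 = 0.5 mg/dL, a fall of 0.5/2.5 = 20%. Assume exponential decline with the same half-life h in every infant. The time from starting value B to 2 mg/dL is t = h × log2(B/2).

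With h = 4 weeks:
- B = 2.6: 4 × log2(1.3) = 1.5 weeks
- B = 5: 4 × log2(2.5) = 5.3 weeks
- B = 8: 4 × log2(4) = 8.0 weeks
- B = 15: 4 × log2(7.5) = 11.6 weeks

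From 2.6 to 15 mg/dL the time differs 7.7-fold with identical treatment. The half-life scales all times but leaves this ratio unchanged. With h between 3 and 12 weeks, the time is 1.1 to 4.5 weeks from 2.6 and 10.0 to 39.9 weeks from 20 mg/dL.

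**Step 2: simulated comparisons with no drug effect.** Group size is 13 per group. Thirteen is the only enrolment figure in the documents (Section 7.0); a comparator group of 13 is assumed. Two sets of assumptions were used, both with weekly sampling:
- *Set A:* entry values lognormal with log-SD 0.5, truncated to above 2.5 (medians below are before truncation); half-life median 4 weeks, log-SD 0.6; censoring at 26 weeks; adjustment for log baseline bilirubin.
- *Set B:* entry value 2.5 plus a lognormal excess with log-SD 0.5; half-life median 6 weeks, log-SD 0.5; follow-up 52 weeks; adjustment for log(log2(B/2)).

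The hazard ratio (HR) is for normalization, Omegaven against comparator. Above 1 favours Omegaven. Rejection means p < 0.05.

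| Set | Median entry, Omegaven vs comparator (mg/dL) | Crude HR | Crude rejection | Adjusted HR | Adjusted rejection |
|---|---|---|---|---|---|
| A | 5 vs 5 | 1.00 | 6-7% | – | 7% |
| A | 5 vs 6 | 1.18 | 6.6% | – | – |
| A | 5 vs 8 | 1.56-1.57 | 18-19% | 0.97-1.01 | 7-8% |
| A | 8 vs 5 | 0.62-0.64 | 21% | 0.97 | 8% |
| B | 5 vs 5 | 1.02 | 7.3% | 1.02 | 7.5% |
| B | 4 vs 6 | 2.08 | 40% | 0.93 | 8.2% |
| B | 6 vs 4 | 0.47 | 44% | 1.05 | 7.3% |

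Ranges are across repeated runs; a dash means no figure is reported. In Set A at 5 vs 8, raising the log-SD of half-life to 1.0 lowers the crude HR to 1.39 and rejection to 12%.

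The adjusted rejection of about 7-8% is also seen with equal entry medians, so it reflects small-sample behaviour of the Cox test and not failed adjustment. Neither set models deaths or transplants; Set B counts a single value below 2 as the event, and Set A is not described as applying the three-consecutive rule.

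**The case against.** The strongest objection is that the key sentence is broken. Words are missing after the drug name, and the total bilirubin sentence points back to a survival analysis description that is not on the page. The word crude often precedes an adjusted analysis. So a reader might infer that the plan rejects adjustment; the text does not support that. It shows only that no adjusted analysis is stated. If one was intended, restoring it is the same edit.

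A reader might also infer that starting differences will show up as a benefit of Omegaven. That does not follow. The bias needs the groups to differ at entry, and it favours whichever group starts lower. Nor do the documents show that infants just above 2.5 mg/dL recover quickly on any emulsion; Section 10.0 expects levels to rise before treatment.

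Third, Hypothesis 2.1 could mean that both groups are timed from first exceeding 2.5 mg/dL, which would narrow starting differences. But Section 10.0 times from baseline, Section 6.0 draws baseline labs just before Omegaven starts, and the comparator's time zero is not defined. This stands as a reason to settle time zero first.

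Fourth, the plan will plot individual profiles and fit longitudinal models. Both are descriptive or exploratory and neither corrects the primary comparison. If only the Omegaven group is analysed for this outcome, there is no between-group confounding; the point then reduces to describing the time curve alongside entry bilirubin.

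Finally, the simulated sizes come from chosen imbalances. That is right, and at medians of 5 vs 6 the distortion is small.

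**Conclusion.** The concern holds in a conditional form. The primary efficacy outcome depends on starting bilirubin, and the stated analysis does not account for it. If the groups differ at entry, the difference can appear as a treatment effect in either direction. Direction and size cannot be known from the documents. Under the assumptions above, with 13 per group and no drug effect, the distortion runs from slight (HR about 1.2, near-nominal rejection) to serious (HR about 2.1, 40% rejection), and reverses sign with the imbalance.

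The missing upper limit is not itself a defect, and eligibility need not change. It only widens the range of starting values that the analysis must handle. This is worth fixing because the needed measurement is already collected and the bias would fall on the primary efficacy result.

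**What to change.** In Section 10.0, efficacy analysis:

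1. State who the comparators are for this outcome and use the same definition of time zero in both groups.
2. Tabulate baseline direct and total bilirubin by group.
3. Make the main analysis of time to direct bilirubin below 2 mg/dL a Cox model with log baseline direct bilirubin as a covariate, taking the last value before time zero.
4. For time to total bilirubin of 1.2, use the same model with log baseline total bilirubin.
5. Keep the crude comparison as supportive, and complete the broken sentence.

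The cost is a few lines of text and one extra parameter in a small sample. Baseline values are already in Table 3 for the Omegaven group; the plan must say that comparators have a value at the matching time.

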Although the pathological features of PNALD have been well described, the etiology, prevention, and treatment of this complication are not well understood. Multiple hypotheses exist to explain the pathogenesis of PNALD including altered gut hormonal profiles (6), the propensity for bacterial translocation in the absence of enteral intake (7, 8), intestinal stasis resulting in the reduced clearance of hepatotoxic bile acids (8), and direct deficiencies or toxic components of the PN solution itself resulting in excessive glucose calorie uptake, excessive lipid infusion, or nutritional deficiencies such as essential fatty acid deficiency (9-11). None of these theories has been confirmed consistently. The etiology of PNALD is currently considered multifactorial. Available treatment options for this disease process are limited and have achieved moderate success at best. Care of the PN-dependent patient is focused on gradually increasing enteral caloric intake as the residual bowel adapts allowing PN to be discontinued (12). In fact, it has been shown both experimentally and clinically that partial enteral nutrition, when tolerated, helps to protect against the development of PNALD (13-15). In severe cases of refractory hepatic failure, liver transplantation with or without accompanying small bowel transplantation remains the only treatment option.

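### The exploratory marker-trend analysis predicts a fall within the Omegaven group but names no post-treatment contrast with soybean, so a fall shared by both groups would satisfy it

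*Combined protocol and SAP*

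**What the plan says.** Section 10.0, Analysis of Efficacy, introduces the trend models as exploratory: "Trends in liver function markers over time will be explored using generalized linear models", with GEE or random effects for repeated measures. Two groups are in the models. For the earlier period it states: "In these models we will hypothesize that for both groups biochemical levels increase for all tests with equal slope before treatment". For the later period it states only: "After treatment, however, levels should be decreasing for patients in the Omegaven™ group". It gives no expectation for soybean infants after baseline, and no interaction term, effect estimate, interval, test or significance level.

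In section 2.0, Hypothesis for Aim 2, the second sentence of 2.1 reads: "Additionally, patients receiving Omegaven™ will experience a decrease in their levels of bilirubin and other hepatic enzymes over time". The first sentence of 2.1, on time to a bilirubin threshold, is comparative: "faster than patients receiving conventional fat emulsions". Hypothesis 2.3, on infection, is comparative too.

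Section 5.0 describes a "non-randomized, open-labeled, prospective study of intravenously administered Omegaven™ fat emulsion". Section 4.0 requires direct bilirubin above 2.5 mg/dL at entry and prior use of standard measures, including enteral advancement and ursodiol. Section 1.0 says that care aims to increase enteral intake as the bowel adapts.

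**The concern.** The plan builds the first half of a difference-in-slopes analysis (two groups, equal slopes beforehand) and stops before the difference. As worded, the prediction depends only on the Omegaven group's own course. It therefore contrasts falling levels with unchanged levels, not Omegaven with soybean.

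This matters because Aim 2 is to be judged on hepatic enzymes as well as bilirubin. The time-to-event outcomes concern bilirubin alone. Apart from plots and a descriptive look at spikes, the trend models are the only analysis in section 10.0 that clearly reaches the enzymes. If their result is reported in the form in which it is predicted, recovery under ordinary care and a drug effect look the same.

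**Working it through.** **1. The prediction in symbols.** Let g be the post-baseline slope that infants would have on soybean, and d the change in slope due to Omegaven. The Omegaven slope is g + d and the soybean slope is g.

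- Prediction as written: g + d < 0. With d = 0 it is met whenever g < 0.
- It can also fail a useful drug. If g > 0 and −g ≤ d < 0, Omegaven slows or halts the rise, which Aim 2 would count as halted progression, yet levels do not fall.
- Contrast: (Omegaven slope after − before) − (soybean slope after − before). With equal slopes before, this equals d whatever g is.

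**2. Can g be negative?** The documents leave it open.

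- For: entry selects on a high bilirubin, so some regression to the mean is expected, and enteral feeding continues to advance. Section 1.0 says that "partial enteral nutrition, when tolerated, helps to protect against the development of PNALD".
- Against: section 1.0 says that abnormalities worsen with time on PN, and section 7.0 expects untreated disease to progress.

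**3. Illustration on the log scale.** The plan has no figure to reproduce. The 13 infants mentioned in section 7.0 are the only enrolment count. Everything else here is assumed: 13 soybean infants, weekly values over weeks 0 to 16, residual SD 0.25, between-infant slope SD 0.05 or 0.08 per week, d = 0, and a two-sided 5% t-test counted only in the favourable direction for both criteria.

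- Sum of squares of weeks 0 to 16 about their mean: 408. Error SD of one infant's slope: 0.25/√408 = 0.0124.
- Total slope SD s: √(0.05² + 0.0124²) = 0.0515, or √(0.08² + 0.0124²) = 0.0810.
- Mean slope for half-life h weeks: −ln 2/h. Noncentrality: mean × √13/s. The one-group criterion is met when t on 12 df is below −2.179.
- Example, h = 16: mean −0.0433. Noncentrality is −0.0433 × 3.606/0.0515 = −3.03, or −1.93 with s = 0.0810. The probability is 80% or 43%.

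| Shared natural course | Omegaven slope significantly below 0 | Omegaven vs soybean slopes |
|---|---|---|
| Rising 1% per week | 1% or less | about 2.5% |
| Flat | 2.5% | about 2.5% |
| Half-life 52 weeks | 8–14% | about 2.5% |
| Half-life 26 weeks | 19–40% | about 2.5% |
| Half-life 16 weeks | 43–80% | about 2.5% |
| Half-life 12 weeks | 66–96% | about 2.5% |
| Half-life 8 weeks | 94–100% | about 2.5% |

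Simulation with 20,000 runs per row gave 2.2 to 2.7% for the contrast.

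**4. Second illustration, in mg/dL per week.** The assumed slope SD is 0.30. At 13 per group, a shared slope of −0.1, −0.2 or −0.3 gives noncentrality −1.20, −2.40 or −3.61, and the one-group criterion is met in 20%, 60% or 91% of trials. At 40 per group the figures are 54%, 98% and 100%. The contrast stays at 2.3 to 2.7%. More infants make the one-group reading worse, because it estimates g + d more precisely and not d.

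Both illustrations use the post-baseline segment only. They show the mechanism and do not model the full before-and-after analysis.

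**The case against.** The strongest reply is that the plan contains no decision rule. It says that trends are explored and gives an expectation, without a test, alpha or criterion for success. That is right. A reader might infer that the plan declares efficacy once the Omegaven slope is below zero at p < 0.05, but no such rule is in the documents. The percentages describe one possible reading and are not the trial's error rate.

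Second, having both groups in the models, an equal-slope premise and the word however all suggest that a contrast was partly intended. This is plausible, and the models could estimate one. It is still not named, and section 2.0 states comparisons openly where it wants them.

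Third, the case for natural decline is limited. The enteral-nutrition statement concerns prevention of liver disease, not reversal. Standard measures had to be in use before entry, with bilirubin still high. With a shared rise the one-group reading almost never misleads. This stands: the direction and size of the shared course are unknown, which is itself a reason to measure it in the comparator.

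Fourth, a reader might attach hypothesis 2.2 to the same defect, since "Patients with surgical gastrointestinal disease and cholestasis will improve clinical hepatic status" also lacks a comparator. Nothing ties that clinical statement to the marker models, so it is left out of the point.

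**Conclusion.** The point holds as a specific defect of an exploratory analysis. Section 10.0 and the second sentence of 2.1 predict a fall in one group and name no contrast after treatment, so a shared fall would satisfy them. This follows from the wording and needs no assumed number.

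Its size is not known. Across the assumed courses from flat to an 8-week half-life, the one-group reading is met in about 2.5 to 100% of trials without a drug effect, against about 2.5% for the contrast. With a shared rise it is met in 1% or less.

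A reader might go further and infer that the trial's efficacy evidence as a whole is uncontrolled. The documents do not support that from this point: the primary efficacy hypothesis is comparative and concerns a different outcome, time to normalization of bilirubin. The change should be made, but it is not grounds to reject the efficacy plan.

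**What to change.** In section 10.0:

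1. Name the estimate: the Omegaven-minus-soybean difference in slope change from before to after baseline (the group-by-period-by-time term), with a 95% CI.
2. Define time zero for soybean infants, for example the first direct bilirubin above 2.5 mg/dL, and apply the same definition in both groups. Any gap between that date and the first Omegaven infusion then counts as post-baseline and should be reported.
3. Extend to these models the confounder adjustment now planned only for the PELD comparisons.
4. State that a fall within the Omegaven group alone is descriptive. If no soybean marker series exists, draw no efficacy conclusion from the trend models.

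In section 2.0, reword the second sentence of 2.1 as a larger fall than in soybean infants.

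The cost is wording, a model term, covariates and usable soybean data before and after time zero. No clinical procedure changes. The interval widens: with 13 per group and slope SD 0.30, the half-width for a post-baseline slope goes from 2.179 × 0.30/√13 = 0.18 to 2.064 × 0.30 × √(2/13) = 0.24 mg/dL per week, and estimating the earlier slopes adds more. The result may look less favourable. The contrast removes a shared fall but not all confounding between non-randomized groups.
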